8. STUDY PROCEDURES

8.1 Schedule of study procedures

Before study entry, throughout the study, and following study drug discontinuation, various clinical and diagnostic laboratory evaluations are outlined. The purpose of obtaining these detailed measurements is to ensure adequate safety and tolerability assessments. Clinical evaluations and laboratory studies may be repeated more frequently if clinically indicated. The Schedules of Assessments during the screening and treatment period is provided following the Protocol Synopsis

8.1.1 Screening Phase

Screening procedures will be performed up to 28 days before Day 1, unless otherwise specified. All subjects must first read, understand, and sign the IRB/REB/IEC-approved ICF before any study-specific screening procedures are performed. After signing the ICF, completing all screening procedures, and being deemed eligible for entry, subjects will be enrolled in the study.

Procedures that are performed prior to the signing of the ICF and are considered standard of care may be used as screening assessments if they fall within the 28-day screening window.

The following procedures will be performed during the Screening Visit:

- Informed Consent
- Review of eligibility criteria
- Medical history and demographics
- Complete physical exam
- ECOG Performance Status
- Vitals signs, weight
- 12-lead ECG (in triplicate [2-5 minutes apart])
- Archived tissue or tumor biopsy
- Review of prior/concomitant medications
- Imaging by CT/MRI
- Clinical laboratory tests for:
 - Hematology (see Table 3)
 - Clinical chemistry (see Table 4)
 - TSH with reflexive free T4
 - Coagulation (PT, aPTT, INR)
 - Creatinine Clearance
 - Serum or urine pregnancy test (for women of childbearing potential only)
 - Urinalysis (see Table 7)

8.1.2 Treatment Phase

Procedures to be conducted during the treatment phase of the study are presented in the Schedule of Assessments. Screening procedures performed within 72 hours of Cycle 1 Day 1 (C1D1) do not need to be repeated on C1D1.

8.1.3 End of Treatment

End of treatment is defined as the last planned dosing visit within the 12-month dosing period. For subjects who discontinue durvalumab or tremelimumab prior to completing all 13 cycles, end of treatment is considered the last visit where the decision is made to discontinue treatment. All required procedures may be completed within \pm 7 days of the end of treatment visit.

Assessments for subjects who have completed durvalumab and tremelimumab treatment and achieved disease control, or have discontinued durvalumab or tremelimumab due to toxicity in the absence of confirmed progressive disease are provided in APPENDIX 2.

Assessments for subjects who have discontinued durvalumab or tremelimumab treatment due to confirmed PD are presented in APPENDIX 3.

All subjects will be followed for survival until the end of the study regardless of further treatments, or until the sponsor ends the study.

8.2 Description of study procedures

8.2.1 Medical history and physical examination, electrocardiogram, weight and vital signs

Findings from medical history (obtained at screening) and physical examination shall be given a baseline grade according to the procedure for AEs. Increases in severity of pre-existing conditions during the study will be considered AEs, with resolution occurring when the grade returns to the pre-study grade or below.

Physical examinations will be performed on study days noted in the Schedule of Assessments.

8.2.2 Physical examination

Physical examinations will be performed according to the assessment schedule. Full physical examinations will include assessments of the head, eyes, ears, nose, and throat and the respiratory, cardiovascular, GI, urogenital, musculoskeletal, neurological, dermatological, hematologic/lymphatic, and endocrine systems. Targeted physical examinations are to be utilized by the Investigator on the basis of clinical observations and symptomatology. Situations in which physical examination results should be reported as AEs are described in Section 10

8.2.3 Electrocardiograms

Resting, triplicate 12-lead ECGs will be recorded at screening and as clinically indicated throughout the study. ECGs should be obtained after the patient has been in a supine position for 5 minutes and recorded while the patient remains in that position.

In case of clinically significant ECG abnormalities, including a QTcF value >470 ms, 2 additional 12-lead ECGs should be obtained over a brief period (eg, 30 minutes) to confirm the finding.

Situations in which ECG results should be reported as AEs are described in Section 10.0.

8.2.4 Vital signs

Vital signs (blood pressure [BP], pulse, temperature, and respiration rate) will be evaluated according to the assessment schedules.

On infusion days, patients receiving durvalumab + tremelimumab treatment will be monitored during and after infusion of IP Per standard clinical practice.

Body weight is also recorded along with vital signs.

Situations in which vital signs results should be reported as AEs are described in Section 10.3.

8.2.5 Clinical laboratory tests

The following clinical laboratory tests will be performed (see the Schedule of Assessments)

- Coagulation parameters: Activated partial thromboplastin time and International normalised ratio to be assessed at baseline and as clinically indicated
- Pregnancy test (female subjects of childbearing potential only)
 - Urine human chorionic gonadotropin (at screening only) OR
 - Serum beta-human chorionic gonadotropin (at screening only)
- Thyroid Stimulating Hormone
 - free T4 only if TSH is abnormal

Table 5. Hematology Laboratory Tests

Basophils	Mean corpuscular volume
Eosinophils	Monocytes
Hematocrit	Neutrophils
Hemoglobin	Platelet count
Lymphocytes	Red blood cell count
Mean corpuscular hemoglobin	Total white cell count
Mean corpuscular hemoglobin concentration	

Table 6. Clinical chemistry (Serum or Plasma) Laboratory Tests

Albumin	Glucose
Alkaline phosphatase	Lactate dehydrogenase
Alanine aminotransferase	Magnesium
Aspartate aminotransferase	Potassium
Bicarbonate	Sodium
Calcium	Total bilirubin ^a
Chloride	Total protein
Creatinine	Urea or blood urea nitrogen, depending on local practice

^a If Total bilirubin is $\geq 2 \times \text{ULN}$ (and no evidence of Gilbert's syndrome) then fractionate into direct and indirect bilirubin

Table 7. Urinalysis Tests^a

Bilirubin	pH
Blood	Protein
Glucose	Specific gravity
Ketones	Colour and appearance

^a Microscopy should be used as appropriate to investigate white blood cells and use the high power field for red blood cells

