1.4.2.3 Durvalumab + tremelimumab

No safety studies in animals have been performed combining tremelimumab with durvalumab. As both CTLA-4 and PD-L1 have mechanisms of actions that enhance activation of immune cells, their potential to induce cytokine release was tested in a whole-blood assay system. Durvalumab and tremelimumab, either alone or in combination, did not induce cytokine release in blood from any donor.

Study D4190C00006: The safety profile of durvalumab and tremelimumab combination therapy in the 102 subjects with advanced NSCLC in Study D4190C00006 is generally consistent with that observed across 177 subjects treated with durvalumab and tremelimumab combination therapy (not including subjects treated with blinded investigational product). As of 15Apr2015, 95 of 102 subjects (93.1%) reported at least 1 AE. All subjects in the tremelimumab 3 and 10 mg/kg dose cohorts experienced AEs; subjects in the durvalumab 20 mg/kg and tremelimumab 1 mg/kg Q4W cohort experienced the lowest AE rate (77.8%). Treatment-related AEs were reported in 74 of 102 subjects (72.6%), with events occurring in $> 10\%$ of subjects being diarrhea (27.5%), fatigue (22.5%), increased amylase and pruritus (14.7% each), rash (12.7%), colitis (11.8%), and increased lipase (10.8%). Treatment-related \geq Grade 3 AEs reported in $\geq 5\%$ of subjects were colitis (8.8%), diarrhea (7.8%), and increased lipase (5.9%). Five subjects reported treatment-related Grade 4 events (sepsis, increased ALT, and increased AST in 1 subject; increased amylase in 2 subjects; myasthenia gravis in 1 subject; and pericardial effusion in 1 subject) and 2 subjects had treatment-related Grade 5 events

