(polymyositis and an uncoded event of neuromuscular disorder [VT]); the Grade 4 event of myasthenia gravis and Grade 5 polymyositis occurred in 1 subject. There were 2 subjects (both in the MEDI4736 20 mg/kg + tremelimumab 3 mg/kg Q4W cohort) with dose-limiting toxicities (DLTs): 1 subject with Grade 3 increased AST, and 1 subject with Grade 3 increased amylase and Grade 4 increased lipase. Fifty-six subjects (54.9%) reported SAEs, with events occurring in > 5% of subjects being colitis (9.8%) and diarrhea (7.8%). Thirty-six subjects (35.3%) experienced treatment-related SAEs. Twenty-seven subjects (26.5%) permanently discontinued treatment due to AEs. Treatment-related AEs resulting in discontinuation in ≥ 2 subjects were colitis (7 subjects), pneumonitis (5 subjects), diarrhea (3 subjects), and increased AST (2 subjects). Additional safety results from this study are presented in Section 1.3.1 and the durvalumab IB.

In the literature (**Error! Reference source not found.**), using the combination of the same class of drugs (eg, anti-PD-1 and anti-CTLA4 antibodies), specifically nivolumab + ipilimumab in a study involving patients with malignant melanoma, the safety profile of this combination had shown occurrences of AEs assessed by the Investigator as treatment-related in 93% of treated patients, with the most frequent events being rash (55% of patients), pruritus (47% of patients), fatigue (38% of patients), and diarrhea (34% of patients). Grade 3 or 4 AEs, regardless of causality, were noted in 72% of patients, with Grade 3 or 4 events assessed by the Investigator as treatment-related in 53%. The most frequent of these Grade 3 or 4 events assessed by the Investigator as treatment-related include increased lipase (in 13% of patients), AST (in 13%), and ALT levels (in 11%). Frequent Grade 3 or 4 selected AEs assessed by the Investigator as treatment-related in the combination therapy included hepatic events (in 15% of patients), GI events (in 9%), and renal events (in 6%). Isolated cases of pneumonitis and uveitis were also observed.

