10.1.3 Durvalumab + tremelimumab adverse events of special interest

An adverse event of special interest (AESI) is one of scientific and medical interest specific to understanding of the Investigational Product and may require close monitoring and rapid communication by the investigator to the sponsor. An AESI may be serious or non-serious. The rapid reporting of AESIs allows ongoing surveillance of these events in order to characterize and understand them in association with the use of this investigational product.

AESIs for durvalumab and tremelimumab include but are not limited to events with a potential inflammatory or immune-mediated mechanism and which may require more frequent monitoring and/or interventions such as steroids, immunosuppressants and/or hormone replacement therapy. These AESIs are being closely monitored in clinical studies with durvalumab monotherapy and combination therapy. An immune-related adverse event (irAE) is defined as an adverse event that is associated with drug exposure and is consistent with an immune-mediated mechanism of action and where there is no clear alternate etiology. Serologic, immunologic, and histologic (biopsy) data, as appropriate, should be used to support an irAE diagnosis. Appropriate efforts should be made to rule out neoplastic, infectious, metabolic, toxin, or other etiologic causes of the irAE.

If the Investigator has any questions in regards to an adverse event (AE) being an irAE, the Investigator should promptly contact the Study Physician.

AESIs observed with durvalumab and tremelimumab include:

- Colitis
- Pneumonitis
- ALT/AST increases / hepatitis / hepatotoxicity
- Neuropathy / neuromuscular toxicity (i.e. events of encephalitis, peripheral motor and sensory neuropathies, Guillain-Barré, and myasthenia gravis)
- Endocrinopathy (i.e. events of hypophysitis, adrenal insufficiency, and hyper- and hypothyroidism)
- Dermatitis
- Nephritis
- Pancreatitis (or labs suggestive of pancreatitis - increased serum lipase, increased serum amylase)

Further information on these risks (e.g. presenting symptoms) can be found in the current version of the durvalumab and tremelimumab Investigator Brochure. For durvalumab and tremelimumab, AESIs will comprise the following:

Pneumonitis

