Cases where a patient shows elevations in liver biochemistry may require further evaluation and occurrences of AST or ALT $\geq 3 \times$ ULN together with total bilirubin $\geq 2 \times$ ULN may need to be reported as SAEs. Please refer to Appendix 1 for further instruction on cases of increases in liver biochemistry and evaluation of Hy's law.

Gastrointestinal disorders

Diarrhea/colitis is the most commonly observed treatment emergent SAE when tremelimumab is used as monotherapy. In rare cases, colon perforation may occur that requires surgery (colectomy) or can lead to a fatal outcome if not properly managed. Guidelines on management of diarrhea and colitis in patients receiving tremelimumab are provided in Table 1.

Endocrine disorders

Immune-mediated endocrinopathies include hypophysitis, adrenal insufficiency, and hyper- and hypothyroidism. Guidelines for the management of patients with immune-mediated endocrine events are provided in Table 1.

Pancreatic disorders

Immune-mediated pancreatitis includes autoimmune pancreatitis, and lipase and amylase elevation. Guidelines for the management of patients with immune-mediated pancreatic disorders are provided in Table 1.

Neurotoxicity

Immune-mediated nervous system events include encephalitis, peripheral motor and sensory neuropathies, Guillain-Barré, and myasthenia gravis. Guidelines for the management of patients with immune-mediated neurotoxic events are provided in Table 1.

Nephritis

Consult with Nephrologist. Monitor for signs and symptoms that may be related to changes in renal function (e.g. routine urinalysis, elevated serum BUN and creatinine, decreased creatinine clearance, electrolyte imbalance, decrease in urine output, proteinuria, etc)

Patients should be thoroughly evaluated to rule out any alternative etiology (e.g., disease progression, infections etc.)

Steroids should be considered in the absence of clear alternative etiology even for low grade events (Grade 2), in order to prevent potential progression to higher grade event. Guidelines for the management of patients with immune-mediated neurotoxic events are provided in Table 1.

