Grade 1 No dose modification	
Grade 2 Hold study drug/study regimen dose until Grade 2 resolution to Grade ≤ 1 . If toxicity worsens, then treat as Grade 3 or Grade 4. Study drug/study regimen can be resumed once event stabilizes to Grade ≤ 1 after completion of steroid taper. Patients with endocrinopathies who may require prolonged or continued steroid replacement can be retreated with study drug/study regimen on the following conditions: 
 The event stabilizes and is controlled. The patient is clinically stable as per Investigator or treating physician's clinical judgement. Doses of prednisone are at ≤ 10 mg/day or equivalent. 	
Grade 3 Depending on the individual toxicity, study drug/study regimen may be permanently discontinued. Please refer to guidelines below.	
Grade 4 Permanently discontinue study drug/study regimen.	
Note: For Grade ≥ 3 asymptomatic amylase or lipase levels, hold study drug/study regimen, and if complete work up shows no evidence of pancreatitis, study drug/study regimen may be continued or resumed.	

**Dosing Modification and Toxicity Management Guidelines for Immune-mediated,
Infusion Related, and Non Immune-mediated Reactions (MEDI4736
Monotherapy or Combination therapy with Tremelimumab or
Tremelimumab Monotherapy) 19 August 2016 Version**

Dose Modifications	Toxicity Management

Note: For Grade 3 and above asymptomatic amylase or lipase levels hold study drug/regimen and if complete work up shows no evidence of pancreatitis, may continue or resume study drug/regimen
	

(i) AE Adverse event; CTC Common Toxicity Criteria; CTCAE Common Terminology Criteria for Adverse Events; irAE Immune-related adverse event; IV intravenous; NCI National Cancer Institute; PO By mouth.
	

Specific Immune-mediated Reactions

Adverse Events	Severity Grade of the Event (NCI CTCAE version 4.03)	Dose Modifications	Toxicity Management
Pneumonitis/ILD	Any Grade	General Guidance	
For Any Grade:
 
 Monitor patients for signs and symptoms of pneumonitis or ILD (new onset or worsening shortness of breath or cough). Patients should be evaluated with imaging and pulmonary function tests, including other diagnostic procedures as described below. Initial work-up may include clinical evaluation, monitoring of oxygenation via pulse oximetry (resting and exertion), laboratory work-up, and high-resolution CT scan.

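### Amylase and lipase elevations are a named special-interest event with a hold rule for asymptomatic values, but no scheduled test measures either enzyme

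*Combined protocol and SAP*

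**What the plan says.** Three parts of the protocol treat the pancreatic enzymes as a safety signal.

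- Section 10.1.3 includes in its list of special-interest events "Pancreatitis (or labs suggestive of pancreatitis - increased serum lipase, increased serum amylase"). Under pancreatic disorders it adds: "Immune-mediated pancreatitis includes autoimmune pancreatitis, and lipase and amylase elevation". Neither entry requires symptoms.
- Appendix 1 states, for Grade 3 or higher, "asymptomatic amylase or lipase levels, hold study drug/study regimen, and if complete work up shows no evidence of pancreatitis", treatment may continue or resume. The note appears twice.
- Section 1.4.2.3 reports the same drug pair in 102 patients with lung cancer. Treatment-related amylase increases occurred in 14.7% and lipase increases in 10.8%. The treatment-related events of Grade 3 or higher seen in at least 5% were "colitis (8.8%), diarrhea (7.8%), and increased lipase (5.9"%). One of the two patients with a dose-limiting toxicity (DLT) was "1 subject with Grade 3 increased amylase and Grade 4 increased lipase".

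The laboratory schedule does not follow through. Section 8.2.5 opens with "The following clinical laboratory tests will be performed (see the Schedule of Assessments") and then gives coagulation, pregnancy and thyroid tests and Tables 5 to 7. The panel headed "Table 6. Clinical chemistry (Serum or Plasma) Laboratory Tests" has 16 analytes, and neither amylase nor lipase appears there or in Tables 5 and 7. The screening list in Section 8.1.1 does not name them. The Schedule of Assessments and Appendices 2 and 3 say only serum chemistry, which leads back to Table 6.

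**The concern.** A rule for asymptomatic values needs a test done in patients without symptoms, and the plan schedules none. The hepatic, renal and thyroid special-interest events each have a scheduled marker (transaminases and bilirubin, creatinine, TSH). The pancreatic one has no marker, and no reason is given.

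Safety is the primary endpoint, so ascertainment matters in three places.

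- **Detection claim.** The sample-size argument in Section 11.3 assumes that an event which occurs is recorded.
- **Decision rules.** Section 6.4 counts any Grade 4 immune-related event as a DLT, counts a Grade 3 one if it does not downgrade in time, and does not exclude enzyme elevations. Section 3.3 counts drug-related Grade 4 events toward halting enrolment. An unmeasured event enters neither count.
- **Baseline.** One branch of the Section 6.4 downgrade test refers to the patient's baseline. Without a screening value, that branch cannot be applied to these enzymes.

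**Working it through.** **Plan's own figure.** Section 11.3 uses 20 patients and 10% prevalence: 1 − (1 − 0.10)^20 = 0.878, which reproduces the stated minimum of 87%. The formula assumes that every event is ascertained.

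**Size if the enzymes were measured in everyone**, at the pooled rates in Section 1.4.2.3:

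- Grade 3 or higher lipase, 5.9%: 20 × 0.059 = 1.18 patients expected.
- At least one in 20: 1 − 0.941^20 = 0.704.
- At least one in the six run-in patients: 1 − 0.941^6 = 0.306.
- Any-grade lipase, 10.8%: 20 × 0.108 = 2.16 patients expected.
- Any-grade amylase, 14.7%: 20 × 0.147 = 2.94 patients expected.

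Both any-grade rates exceed 10%, so the enzymes fall within the class of toxicities that the 87% statement covers.

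**Effect of incomplete ascertainment.** Let s be the share of events picked up by unscheduled testing. The documents give no value for s, so this is a range of assumptions. The chance of recording at least one event is 1 − (1 − p·s)^n.

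| s | p = 10%, n = 20 | p = 5.9%, n = 20 | p = 5.9%, n = 6 |
|---|---|---|---|
| 0 | 0% | 0% | 0% |
| 0.10 | 18% | 11% | 3% |
| 0.25 | 40% | 26% | 9% |
| 0.50 | 64% | 45% | 16% |
| 1 | 88% | 70% | 31% |

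Only full ascertainment returns the plan's figure.

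**Lower rate at this trial's dose.** The 5.9% pools all cohorts, including tremelimumab above 1 mg/kg. Section 1.4.2.4 equates this trial's 75 mg with 1 mg/kg. The documents give no enzyme rate for that cohort. If the rate were 2% (assumption), the chance of at least one event in 20 is 1 − 0.98^20 = 0.332.

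**The case against.** The strongest reply is that the plan does not prevent detection. The Schedule of Assessments allows assessments as clinically required, Section 6 allows procedures at unscheduled times, and Section 8.1 allows more frequent laboratory studies when clinically indicated. The Appendix 1 rule works on any value obtained. This stands. A reader might infer that these events cannot be seen, held for or counted at all, and the documents do not support that. They support only that no scheduled test looks for them. The permission helps with symptomatic patients but does little for the asymptomatic ones the rule addresses.

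The second reply concerns size. The 1.2 patients, 70% and 31% count every Grade 3 or higher lipase event, including symptomatic ones that would prompt testing, and they come from a mix of doses. They are upper bounds on what the gap hides at the source rate. They are not confidence limits, and they cover lipase only. A reader might also take the source-study DLT as evidence for this regimen. Section 1.4.2.3 places both DLT patients in the tremelimumab 3 mg/kg cohort, and Section 1.3.1 reports no DLT among the 11 patients given 20 mg/kg durvalumab with 1 mg/kg tremelimumab.

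The third reply concerns bias. A reader might infer that the primary toxicity result is biased low against the 17% benchmark in Section 11.3. The documents do not say whether that 17% includes enzyme events, and a missed event changes a patient-level rate only if the patient has no other qualifying toxicity. The bias is therefore conditional. Nor would every asymptomatic Grade 3 value be a DLT, because the time limits for downgrading in Section 6.4 apply.

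**Conclusion.** The point holds in limited form. The special-interest definition and the Appendix 1 rule presuppose enzyme values that no scheduled test supplies. Followed as written, the plan leaves most asymptomatic elevations unascertained, provides no baseline, and makes a detection statement that is not valid for these events.

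For Grade 3 or higher lipase the effect is at most about 1.2 of 20 patients at the pooled 5.9% rate, with a 70% chance of at least one in 20 and 31% in the run-in. At an assumed 2% the 20-patient chance is 33%. The share of events without symptoms, the rate at this dose and the yield of unscheduled testing are all unknown from the documents. The inconsistency itself depends on none of them. It should be corrected before the safety claim is relied on, but it does not show that the overall toxicity rate will be understated.

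**What to change.** Reconcile Table 6 and the Schedule of Assessments with Section 10.1.3 and Appendix 1, in one of two ways.

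1. **Measure them.** Add amylase and lipase to Table 6, so that they run on the chemistry sample already drawn at screening, dosing visits and end of treatment. This supplies a baseline and lets the existing rule operate. An unqualified addition would also apply at week 3 of cycle 1 and at the Day 30 follow-up visit, so the sponsor should say whether that is intended.
2. **Limit the claim.** State that the enzymes are not routinely measured, and exclude asymptomatic elevations from the safety conclusion and from the 87% detection statement in Section 11.3 and the synopsis.

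The first option needs two more assays and no extra visit or blood draw. Its real cost lies downstream. More laboratory-only events will be recorded, each value of Grade 3 or higher triggers the existing hold and work-up, and some may count toward the DLT rule and the Grade 4 stopping rule. The second option costs nothing in conduct but narrows what the trial can say. Neither changes any dose, hold or discontinuation rule, and the choice is the sponsor's.
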